***Note:** When MRI Settings are enabled, sensing is disabled. Determine whether or not the subject requires pacing support during the MRI scan. When pacing support is needed, thoracic MRI scan cannot be performed, as *patient doesn't meet inclusion criteria he/she should be immediately withdrawn from the study*. When pacing support is not needed, set the MRI Mode to Pacing Off.

For more details, kindly refer to MRI Ready Systems Manual: MRI Procedure Information for the St. Jude Medical™ MR Conditional System.

In MR Conditional ICDs, tachytherapy is disabled when the MRI settings are programmed.

After the electrical measurements for the RV lead have been taken, capacitor maintenance has been performed, the MRI Checklist (on the programmer) verified and the MRI Setting saved, activate the MRI parameters.

Setting up Pulse Oximetry and ECG

Set up pulse oximetry and an ECG per standard of care.

Place the oximetry clip on the subject's finger or other any other appendage that results in valid pulse oximetry readings. Position MRI compatible surface electrodes on the subject to ensure the subject's heart rate can be continuously monitored during the scan. During the MRI scan, periodically record heart rate, and blood oxygen saturation levels. Visually examine the ECG during the MRI scan. Note any abnormalities observed in the cardiac rhythm. After the MRI scan, remove the subject from the MRI field.

Clinical Investigation Plan

Data Submission

Once required testing has been performed, complete and submit the appropriate forms to St. Jude Medical. Refer to **Table-1 Specific Study Procedures and Data Collection**

Upload pre-MRI scan device session records through the EDC study portal. It is recommended that the following device printouts and measurements be maintained at the site.

- FastPath Summary
- Test Results with Freezes, Include Battery & Leads
- Wrap-up Overview with full parameters
- Upload device session record (X-file) through the EDC study site portal

4.6.1.2 The MRI Scan

After confirmation by the electrophysiologist or device specialist that all pre-MRI system checks (mentioned above) have been met, subjects will have their MRI scan completed by a radiology staff member. **Note: If the patient does not pass the Pre-MRI scan System Check specified above, then the patient should not undergo an MRI scan. The patient can be rescheduled to come back to repeat the Pre-MRI scan System Check testing within the visit window.**

Protocol required MRI scan sequences for each subject undergoing an MRI scan are described in detail in Appendix E. It is recommended that the MRI scan be set up on the MRI scanner in advance of the first subject scheduled for a study scan to ensure the scan has been appropriately programmed, and to provide adequate time to address any questions or issues that may arise.

Subjects will undergo Thoracic MRI scan for the study. The thoracic scan is RF intensive should be set up to last about 6 minutes and 15 seconds. The thoracic scan will need to be repeated four times to ensure the subject is scanned approximately 25 minutes.

In addition to study specific Thoracic MRI Scan, an optional non-study MRI scan (either a brain, cardiac or lumbar scan without administration of contrast agents or sedation) may be run per discretion of Investigator to provide a MRI report to subjects. These optional scans will occur after the study scan and will not have a scan time greater than 5 minutes. Sites will be provided with a guidance document for Optional MRI Scan set-up.

Further details about the set-up, programming and ways to adjust the parameters for MRI scans can be found in Appendix E: MRI Scan Guidelines.

**Clinical Investigation Plan**

The subject may be in the bore or near the vicinity of the magnet for approximately 60 minutes. The actual amount of time the subject will be scanned is approximately 30 minutes (including Optional MRI Scan).

In conditions where the time of RF exposure is stretched above 30 minutes, the scan will be interrupted and patient will be taken out of the MRI bore. MRI scan can be continued again once waiting period of 30 minutes is completed.

The MRI scan is not intended to be diagnostic in nature and therefore the administration of contrast fluids or sedation are not permitted.

Consult the "MRI Ready Systems Manual: MRI Procedure Information for the St. Jude Medical™ MR Conditional System" for guidelines and 'precautions related to conducting an MRI scan with the implanted study ICD system.

NOTE: MRI scan in this study is being performed to demonstrate performance of St. Jude Medical™ MR Conditional ICD System for an MRI scan, and is not meant to be diagnostic in nature. The MRI scan will not be read by the radiologist.

If subject movement causes distortion on the MRI, do not repeat the MRI scan.

Cardiac Monitoring

During the entire MRI scan, the subject's cardiac function must be monitored using pulse oximetry and an ECG by a trained electrophysiologist, cardiologist, or Advanced Cardiac Life Support (ACLS) trained personnel capable of delivering external cardiac pacing defibrillation and advanced cardiac life support. Verbal communication with the subject must also take place to assess and/or confirm any clinically significant changes noted in the subject's oxygen saturation or heart rate, as well as any clinically significant complaints not obvious with pulse oximetry. Record these changes and complaints during the MRI scan.

ACLS procedures must be in place to address situations where a life threatening arrhythmia and/or hemodynamic collapse occurs. The programmer must be used outside the American College of Radiology (ACR) defined Zone 4 magnet room. If the subject's hemodynamic function is compromised during the MRI scan, discontinue the MRI procedure and take proper measures to restore the subject's hemodynamic function.

Clinical Investigation Plan

Handling of Subjects Unable to Tolerate an MR Scan

In cases where the scan cannot be tolerated by the subject, remove the subject from the scanner. Assess the subject for possible adverse events, and treat the subject's reported symptoms according to your institution's standard of practice. Document the reason for the intolerance. At a minimum, information related to the sequence used to perform the scan, the length of time the subject was scanned, and the whole body SAR level reached should be collected and submitted to St. Jude Medical. A repeat scan is not required to be completed. The subject is not withdrawn from the study. The subject should be scheduled to return for their 1 month post MRI scan visit.

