5.1 Primary Endpoint**5.1.1 Primary Endpoint and Hypothesis**

The primary endpoint is the Freedom from MRI scan-related complications related to St. Jude Medical™ MR Conditional ICD System from MRI scan to 1 month post MRI scan

Hypothesis

The hypothesis is formally expressed as:

$$H_0: P_{MRI-Scan} \leq 90\%$$

$$H_a: P_{MRI-Scan} > 90\%$$

Where $P_{MRI-Scan}$ is the freedom from MRI scan-related complications(s) related to St. Jude Medical™ MR Conditional ICD System from MRI scan to 1 month post-MRI scan visit.

The hypothesis will be tested at the 2.5% significance level. The null hypothesis will be rejected if the 97.5% lower confidence bound (LCB) for $P_{MRI-Scan}$ is greater than 90%.

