5.1.1.3 Analysis Populations

The analysis will be conducted on subjects who meet all of the following criteria:

- Implanted with the SJM MR Conditional ICD system
- Sign informed consent
- Meet the MRI Conditions of Use
- Undergo a MRI scan
- Have 1 month post MRI scan visit or have MRI-scan related complication(s) related to SJM MR Conditional ICD system before the 1 month post MRI scan visit

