5.2 Descriptive Endpoints

- Demographics and medical/surgical history such as gender, age, history of smoking, cardiac disease history, arrhythmia history, and indication for ICD implant, etc. Continuous variables will be summarized as sample size, mean, standard deviation, minimum and maximum. For categorical variables, the counts and percentages of subjects will be summarized for each category.
- Proportion of SJM high voltage lead implanted with SJM MR Conditional ICD with capture threshold increase of $\leq 0.5V$ @ 0.5ms from pre-MRI scan testing to 1 month post-MRI scan testing.
This proportion will be calculated as number of subjects who had high voltage lead with

[REDACTED]

Clinical Investigation Plan

capture threshold increased of $\leq 0.5V$ @ 0.5ms from pre-MRI scan testing to 1 month post-MRI scan testing divided by total number of subjects who had high voltage lead implanted, undergo a MRI scan and with both pre-MRI scan and 1 months Post MRI scan capture threshold available.

- Proportion of SJM high voltage lead implanted with SJM MR Conditional ICD with sensing amplitude decrease of $\leq 50\%$ from pre-MRI scan testing to 1 month post-MRI scan testing. This proportion will be calculated as number of subjects who had high voltage lead with sensing amplitude decrease of $\leq 50\%$ from pre-MRI scan testing to 1 month post-MRI scan testing divided by total number of subjects who had high voltage lead implanted, undergo a MRI scan and with both pre-MRI scan and 1 months Post MRI scan sensing amplitude available.
- Average and Peak Specific Absorption Rate (SAR) during MRI scan, MRI visit duration in MRI laboratory and total MRI scan duration in MRI laboratory
Average and Peak Specific Absorption Rate (SAR) during MRI scan, MRI visit duration in MRI laboratory and total MRI scan duration in MRI laboratory will be summarized as mean, standard deviation, minimum, median and maximum.
- Adverse events and death
The number of events, number of subjects who encountered the events will be summarized for each event category for ADE and SADE separately. The number of death will be summarized as counts and percentages for each primary cause.

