5.6 Timing of Analysis

The analysis will be conducted for each phase separately. The dataset will be frozen for analysis for each phase when 168 subjects have completed the 1 month post MRI scan visit.

Success Criteria

Success will be assessed for SJM MR Conditional ICD system in an MRI environment for each phase separately, i.e. safety of SJM MR Conditional ICD system will be established if the primary endpoint is met for each phase, respectively.

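### Does counting subjects with an aborted thoracic scan in the primary analysis, with no full-exposure analysis planned, undermine the safety conclusion?

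*Combined protocol and SAP*

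**What the plan says.** Section 4.6.1.2 sets the intended exposure. One thoracic run lasts about 6 minutes 15 seconds, and "The thoracic scan will need to be repeated four times to ensure the subject is scanned approximately 25 minutes". The same section foresees early stops. Under cardiac monitoring, if haemodynamic function is compromised, staff are to "discontinue the MRI procedure and take proper measures". Under the heading on subjects unable to tolerate the scan, the subject is removed and assessed, and "A repeat scan is not required to be completed. The subject is not withdrawn from the study". The reason, the sequence, the time scanned and the whole-body SAR reached are to be recorded, and the 1-month visit goes ahead.

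Section 5.1.1.3 defines the analysis population by five conditions: the implanted system, consent, the MRI Conditions of Use, "Undergo a MRI scan", and a 1-month visit or an earlier qualifying complication. It states no minimum number of runs, duration or SAR. The scan guidelines (Appendix E) are held under separate cover.

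Section 5.1.1 tests freedom from complications against 90% in each phase: "The hypothesis will be tested at the 2.5% significance level", using an exact Clopper-Pearson lower bound. Section 5.6 freezes each phase at 168 completed 1-month visits and concludes that "safety of SJM MR Conditional ICD system will be established if the primary endpoint is met for each phase, respectively". Section 5.1.1.4 plans no subgroups. In 5.2, exposure is described only overall: "total MRI scan duration in MRI laboratory will be summarized as mean, standard deviation, minimum, median and maximum".

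**The concern.** The study scan is a deliberate, RF-intensive dose of exposure. A subject who leaves the scanner after one run has received about a quarter of it, yet carries the same weight in the binomial proportion as a subject who received all four. If partial scans are less risky, they add easy successes, and a pass might not describe the full 25-minute exposure. If scans are stopped because of device heating or haemodynamic symptoms, the effect could run the other way. With no definition of a completed scan and no analysis split by completeness, the safety statement in 5.6 could be read as covering an exposure that some analysed subjects never had.

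**Working it through.** **Inputs from the documents.** Performance goal 90%; 97.5% lower bound, exact Clopper-Pearson (5.1.1, 5.1.1.1); 168 subjects with a 1-month visit per phase (5.6), taken here as the analysed number; 4 runs of 6.25 minutes (4.6.1.2), and 4 × 6.25 = 25 minutes, as the plan says.

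**Inputs assumed.** The number of aborted scans, m = 3, 8 or 17 (2%, 5% or 10% of 168); the risk in an aborted scan relative to a full one, r = 0, 0.5, 1 or 2; and the true complication rate. The sample-size section is redacted, so no design rate can be taken from it.

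**Step 1: the decision rule.** With f failures among n, the lower bound is the 2.5% quantile of Beta(n − f, f + 1). At n = 168, 9 failures give 90.07% (pass) and 10 give 89.33% (fail). The attained level is P(X ≤ 9) for X ~ Bin(168, 0.10), which is 2.33%. The test holds its level for the hypothesis as written, whichever scanned subjects make up the 168.

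**Step 2: how far aborted scans could shift a pass.** Put the full-scan complication rate exactly at the 10% boundary. The chance of passing is P(X_full + X_abort ≤ 9), with X_full ~ Bin(168 − m, 0.10) and X_abort ~ Bin(m, 0.10 r).

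| Relative risk r in aborted scans | m = 3 | m = 8 | m = 17 |
|---|---|---|---|
| 0 | 2.8% | 3.6% | 5.7% |
| 0.5 | 2.5% | 2.9% | 3.7% |
| 1 | 2.3% | 2.3% | 2.3% |
| 2 | 2.0% | 1.5% | 0.8% |

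The direction depends on r, which nobody knows in advance. The top row is the worst case for the plan.

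**Step 3: what would turn a pass into a completers-only failure.** Suppose every event falls in a completer. The completers-only bound drops below 90% in these cases:

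- 9 events: from 2 aborts (9/167 gives 90.02%, 9/166 gives 89.96%).
- 8 events: from 15 aborts, 9% of 168 (8/154 gives 90.02%, 8/153 gives 89.96%).
- 7 events: from 28 aborts, 17% of 168 (7/141 gives 90.04%, 7/140 gives 89.97%).

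So the two analyses disagree only when the event count is at or near the limit of 9.

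**Step 4: how often they would disagree.** Take r = 0 again. Let k be the most failures that pass among 168 − m completers: 8 of 165, 8 of 160, 7 of 151. The chance that the primary passes and the completers-only bound fails is P(k + 1 ≤ X ≤ 9), X ~ Bin(168 − m, p).

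| Assumed full-scan complication rate p | m = 3 | m = 8 | m = 17 |
|---|---|---|---|
| 1% | under 0.02% | under 0.02% | under 0.02% |
| 2% | 0.4% | 0.4% | 1.0% |
| 4% | 9.0% | 8.3% | 17.6% |

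**Step 5: what a completers-only bound would measure.** At a true 96% freedom from complications in completers, well above the goal, that bound exceeds 90% with probability 78.3% at n = 165, 80.7% at n = 160 and 74.1% at n = 151, against 86.2% at n = 168. The value at 165 is lower than at 160 although the sample is larger, because the cut-off moves in whole events. Losing three subjects costs 86.2 − 78.3 = 7.9 percentage points even if exposure has no bearing on outcome. Much of the 4% row in Step 4 is therefore lost sample size and discreteness, not information about exposure.

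**The case for a change.** The strongest case for a change is that this trial makes a safety claim about an exposure, so the exposure delivered is central. The words of 5.1.1.3 leave the status of a partial scan open. Overall summaries of scan duration do not show whether events fell in full or partial scans. Settling the counting rule in advance would prevent a choice made after the data are seen, and it would cost one sentence and one table on data already collected.

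Parts of this stand. The wording is undefined in the visible text, although a rule in the separately held guidelines or the Conditions of Use cannot be excluded. No planned table links outcome to completeness.

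The rest does not carry a change. The objective in 3.2 concerns patients undergoing a thoracic scan, not patients completing four runs. The protocol also keeps intolerant subjects in the study and brings them back at 1 month, so counting everyone scanned is the natural reading, and it is also the sound one. A full-exposure set would select on something that happens after the scan starts, possibly because of symptoms, and could hide harm. Limiting the safety statement whenever the smaller set's bound failed to exceed 90% would make that set a second success criterion in practice, one that lost sample size alone can trip.

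**Conclusion.** The observation is accurate, but it calls for no change. It describes a missing detail that analysts would fill sensibly: count every subject whose study scan was started and who meets the other conditions, and report aborted scans with their reasons, duration, SAR and outcome. The protocol already collects those items for aborted scans, and 5.2 will report the minimum and median scan duration. Such a table can go in the study report without altering the test, its level or the sample size.

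In the worst case of no risk in aborted scans, and with 3 to 17 of them among 168, the primary and completers-only conclusions would differ with probability 0.4% to 1.0% at a 2% complication rate, practically never at 1%, and 8% to 18% at 4%. These figures rest on assumed abort counts and complication rates, since the documents give none. If aborted scans proved very common and the event count sat close to 9, the report would need to say that the result describes scans as performed. That is a matter of interpretation when the data are in, and it does not make the planned analysis wrong.

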4.6.1.3 Post- MRI Scan Testing

Device Assessment and Programming

Following the MRI Scan, remove the subject from the MRI bore. Interrogate the ICD. Disable the MRI Settings. **Note: MRI settings must be disabled to ensure that tachyarrhythmia therapy is turned back on.** Obtain the following for the ventricular lead:

- In-clinic ventricular bipolar capture threshold at a pulse width of 0.5 ms. Either the manual decrement or automatic (in-clinic, programmer-based) method may be used to obtain the capture threshold.
- In-clinic ventricular bipolar sensing amplitude. Either the incremental or the automatic (in-clinic, programmer based) method may be used to obtain the sensing threshold.
- In clinic ventricular bipolar lead impedance
- In-clinic High Voltage Lead impedance

NOTE: RV capture thresholds are not required to be obtained if a high ventricular rate is present. RV sensing measurements are not required if the subject's intrinsic rate is established to be ≤30 beats per minute.

Reporting of MRI Scan-Related Adverse Device Effects

An ADE or SADE related to the following should be reported as soon as possible to St. Jude Medical: clotting, pulmonary embolism, or heating of the device pocket during the MRI scan. These events are likely to be associated with symptoms occurring during or immediately following the MRI scan and may manifest as chest pain, shortness of breath, or changes in vital signs during or immediately following the MRI scan.

To ensure all ADEs or SADEs related to or caused by the MRI scan are appropriately captured, before starting the scan, verbally instruct the subject to report symptoms of chest pain, shortness of breath or pocket discomfort that he/she experiences while being scanned or immediately after exiting the scanner. Note changes in vital signs such as changes in heart rate, room air blood oxygen saturation, and/or

Clinical Investigation Plan

respiration rate that occur during the MRI scan that may suggest an ADE or SADE has occurred due to clotting, pulmonary embolus or related to lead tip or device pocket heating.

If symptoms during or immediately after the MRI scan suggest that an ADE or SADE has occurred due to clotting, pulmonary embolus or related to lead tip or device pocket heating, test to assess possible causes. Diagnostic testing may be performed in any order deemed appropriate by the investigator; if any test was not performed, provide medical justification for not performing that test:

- (1) A 12-lead ECG
- (2) A 2-view chest X-ray (PA and Lateral).
- (3) Room air blood oxygen saturation
- (4) A transthoracic echocardiogram.

If the subject reports pocket discomfort, ask the subject for additional descriptive information and determine if the pocket is discolored or warm to the touch. ECG, chest x-ray, room air blood oxygen saturation, or transthoracic echocardiogram testing are not required to be performed for symptoms related to device pocket heating.

Data Submission

Once required testing has been performed, complete and submit the appropriate forms to St. Jude Medical. Refer to **Table-1 Specific Study Procedures and Data Collection**.

Export the study MRI scan onto a CD, or other form of electronic media in DICOM format as source document. Upload post MRI scan device session records through the EDC study portal. It is recommended that the following device printouts and measurements be maintained at the site.

- FastPath Summary
- Test Results with Freezes, Include Battery & Leads
- Wrap-up Overview with full parameters
- Upload device session record (X-file) through the EDC study site portal

4.6.2 One (1) Month Post Scan Visit

Testing

Interrogate the ICD and obtain the following for the ventricular lead:

- In-clinic ventricular bipolar capture threshold at a pulse width of 0.5 ms. Either the manual decrement or automatic (in-clinic, programmer-based) method may be used to obtain the capture threshold.
- In-clinic ventricular bipolar sensing amplitude. Either the incremental or the automatic (in-clinic, programmer based) method may be used to obtain the sensing threshold.

Clinical Investigation Plan

- In clinic ventricular bipolar lead impedance
- In-clinic High Voltage Lead impedance

Evaluate the subject for ADE & SADE and submit an AE CRF if applicable.

NOTE: RV capture thresholds are not required to be obtained if a high ventricular rate (e.g. 110bpm) is present. If available, sites should use the automatically obtained pacing capture threshold from the most recent archival data as a substitute for the in clinic capture threshold. RV sensing measurements are not required if the subject's intrinsic rate is established to be ≤30 beats per minute.

Data Submission

Once required testing has been performed, complete and submit the appropriate forms to St. Jude Medical. Refer to **Table-1 Specific Study Procedures and Data Collection**. It is recommended that the following device printouts and measurements be maintained at the site.

- FastPath Summary
- Test Results with Freezes, Include Battery & Leads
- Wrap-up Overview with full parameters
- Upload device session record (X-file) through the EDC study site portal

4.7 Unscheduled Visits

An unscheduled visit is defined as a visit that occurs after Enrollment visit where the subject is seen in clinic due to an ADE or, SADE associated with St. Jude Medical™ MR Conditional ICD System.

Where possible, perform a device interrogation for ventricular lead(s) to obtain:

- In-clinic ventricular bipolar capture threshold at a pulse width of 0.5 ms.
- In-clinic ventricular bipolar sensing amplitude. Either the incremental or the automatic (in-clinic, programmer based) method may be used to measure the sensing threshold.
- In-clinic ventricular bipolar lead impedance
- In-clinic High Voltage lead impedance

Data Submission

Once testing has been performed, complete and submit the appropriate forms to St. Jude Medical. Refer to **Table-1 Specific Study Procedures and Data Collection**.

It is recommended that the following device printouts and measurements be maintained at the site.

- FastPath Summary
- Test Results with Freezes, Include Battery & Leads
- Wrap-up Overview with full parameters
- Upload device session record (X-file) through the EDC study site portal

Clinical Investigation Plan

